	
 
Number of days ventilated and the requirement for invasive/non-invasive methods
 
						
	4 30 day and 3 month mortality						
	5. Complications and safety data associated with SAP						
	6. Opiate consumption such as morphine and related compounds						
	7. Length of stay in hospital and critical care level two/three facility						
	8. Hospital re-admission within 30 days of discharge						
	9. Patient-Reported Outcome Measures (PROMs) at 1 and 3 months:						
	• EQ-5D-5L						
	
 
Medical Research Council (MRC) dysphoea scale at 3 months only
 
						
	
 
Brief Pain Index (BPI)
 
						
	
 
McGill Pain Questionnaire (SF-MPQ-2)
 
						

<sup>1 The blinded end point review committee will make their diagnosis based CPIS and all available trial realted clinical information

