#### 8.2.2.Secondary Outcomes

The secondary outcomes for the ERASER trial are as follows:

- 1. Reduces pain
  - Numerical rating scale (0-10), recorded average every 4 hours on days 1 to 5, day 14 and before discharge.
  - Patient reported brief pain index (BPI) at 1 and 3 months post randomisation.
- 2. Improves ventilatory function
  - Incentive spirometry peak expiratory flow twice a day
- 3. Reduces the number of days ventilated and the requirement for invasive/non-invasive methods
  - Number of days ventilated
  - Type of ventilation invasive/non-invasive
- 4. Improves mortality
  - Mortality measured at 1 and 3 months post randomisation
- 5. Is safe and doesn't have unforseen Complications
  - Measured by SAEs review from randomisation until discharge
- 6. Impacts opiate consumption such as morphine and related compounds
  - Participant opiate consumption measured at discharge and 3 months post randomisation
- 7. Reduces length of hospital stay
  - Length of stay in hospital
  - Length of stay in critical care level two/three facility
- 8. Reduces hospital re-admission within 30 days of discharge
  - Measured by any hospital re-admission within 30 days of discharge

<sup>4 The blinded end point review committee will make their diagnosis based CPIS data and all available trial related clinical information

- 9. Impacts Patient-Reported Outcome Measures:
  - $\circ~$  EQ-5D-5L at 1 and 3 months post randomisation.
  - MRC dyspnoea scale at 3 months post randomisation.
  - o BPI at 1 and 3 months post randomisation.
  - SF-MPQ-2 at 1 and 3 months post randomisation

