# 10.2. AE/SAE REPORTING PERIOD

The reporting period for AEs and Serious Adverse Events (SAEs) in the trial will be from the day that the trial intervention was started until the end of the trial follow up period.

<sup>5 The term life-threatening is defined as diseases or conditions where the likelihood of death is high unless the course of the disease is interrupted.

<sup>6 Medical events that may not be immediately life-threatening or result in death or hospitalisation but may jeopardise the patient or may require intervention to prevent one of the other outcomes listed in the above definitions.

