## 10.3. ADVERSE EVENTS IN ERASER

Participants that meet the eligibility criteria for the ERASER Trial will likely have suffered significant trauma and as a result may experience numerous AEs. As these events are well characterised, it is highly unlikely that these AEs will reveal any new safety information relating to the trial intervention, SAP. Due to this, events that meet the definition of an AE but not an SAE (see table 2) will not be required to be reported to the trial team, these AEs should however be recorded as per local practice.

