#### 10.4.1. SAEs not requiring reporting

Several events that meet the definition of an SAE will not require reporting on the trials dedicated SAE form. If any of the events outlined below in table 3 occur during an individual's participation, from the date that trial intervention started through to end of follow-up, reporting the event on a SAE form is not required as the SAE is not considered to be critical to evaluations of the safety of the trial.

Expected SAE	Process
Pre-planned hospitalisation	Document in medical notes only
SAEs relating to a pre-existing medical condition or those that have occurred as a result of the participants injuries which are unrelated to MRF	Document in medical notes only

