#### 10.4.2. SAEs requiring non-expedited reporting

Where the safety profile is well established, the causal relationship between the intervention (or the participant's underlying condition), and the SAE, may be known. That is, such events are protocol-defined as "expected".

Such events should still be recorded by the site research team in the participant's medical notes and reported to the ERASER Trial Office, but it does not require expedited reporting (immediately on the site becoming aware of the event) since the assessment of expectedness for the specified events has been pre-defined. These SAEs can be reported alongside follow up CRFs at 1 or 3 months post randomisation. These expected SAEs are listed in Table 4 below.

Expected SAE ID	Expected SAE	Process
01	Hospital admissions lasting less than 24 hours	
02	Death - The cause of which is unrelated to intervention	
03	Organ failure – as indicated by SOFA score	
04	Infection to insertion site	Report on SAE Form and
05	Sepsis	provide to the ERASER Trial Office along with follow-up
06	Septic shock	CRFs.
07	Failure of extubation attempt	
08	New clinical diagnosis of pneumonia	
09	Primary cardiac bradyarrythmias and tachyarrythmias	

Table 4: ERASER Trial SAEs requiring non-expedited reporting

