#### 11.1.1. Case Report Form Completion

The CRFs will include, but will not be limited to, the following forms in Table 9.

Form Name	Schedule for submission
Consent form	As soon as eligibility has been confirmed
Randomisation form	At the point of randomisation
Hospital admission form and Baseline form	Immediately following randomisation (Day 0)
Daily Assessment	Daily until day 30 or discharge
1 month and 3 month Follow-up CRFs	1 month and 3 months post-randomisation
	If expedited: emailed within 24 hours of site research team
	becoming aware of event
Serious Adverse Event Form	
	If non-expedited: emailed within 4 weeks of site research
	team becoming aware of event
Dragnangy notification Form	As soon as possible after becoming aware of participant's
Pregnancy notification Form	pregnancy
Change of status Form	As soon as possible after the point of notification or death

Table 9: ERASER Trial CRFs

A CRF should be completed for each individual participant.

In all cases, it remains the responsibility of the PI to ensure that the CRFs have been completed correctly and that the data are accurate.

The trial Site Signature and Delegation Log will identify the research team members with responsibilities for data collection. The delegated staff should ensure the accuracy, completeness and timeliness of the data reported.

Data reported on each form should be consistent with the source data and any discrepancies will be explained. All missing and ambiguous data will be queried. Staff delegated to complete CRFs will be trained to adhere to trial CRF completion guideline.

The following guidance applies to data and partial data:

- Only CRFs provided by the ERASER Trial Office should be used
- Date format and partial dates all dates should be in the format of DD/MMM/YYYY
- Time format all times should be in accordance with the 24-hour clock
- Rounding conventions should be to the nearest whole number: number ending 5-9 to be rounded up; number ending 1-4 to be rounded down.
- Trial-specific interpretation of data fields
- Entry requirements for concomitant medications use generic names where possible
- Trial specific interpretation of data fields where guidance is needed, additional information will be supplied
- Repeat laboratory tests if a test is repeated, it is either to confirm or clarify a previous reading. Confirmatory tests should use the original test values
- Protocol and GCP non-compliances should be reported to the ERASER Trial Office on discovery

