## 14.3. PLANNED FINAL ANALYSES

The primary analysis for the study will occur once all participants have completed the 3-month postrandomisation assessment and corresponding outcome data has been entered onto the study database and validated as being ready for analysis. This analysis will include data items up to and including the 3 month assessment and no further.

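### The safety outcome and the SAE reporting period use different windows, and the reporting start is not clearly defined for usual-care participants or for block-arm participants whose catheter is never inserted

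*Protocol*

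**What the plan says.** On the outcome, the Trial Summary lists secondary outcome 5 as "Complications and safety data associated with SAP". Section 8.2.2 makes it operational as "Measured by SAEs review from randomisation until discharge".

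On reporting, section 10.2 runs the AE/SAE period "from the day that the trial intervention was started until the end of the trial follow up period". Section 10.4.1 repeats this for exempt SAEs: "from the date that trial intervention started through to end of follow-up". Section 9.1.2 has sites begin monitoring once the participant is randomised and the allocated treatment starts, in the manner set out in section 10.

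On non-serious events, section 10.3 says that they "will not be required to be reported to the trial team", although sites record them locally. Sections 9.1.3 and 9.1.4 and Table 1 nevertheless list adverse events among the trial data, through the hospital stay and at months 1 and 3 (Table 1 also marks them at discharge).

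On deadlines for non-expedited SAEs, section 10.4.2 says: "These SAEs can be reported alongside follow up CRFs at 1 or 3 months post randomisation". Table 9 in section 11.1.1 says: "If non-expedited: emailed within 4 weeks of site research" team awareness.

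**The concern.** Section 2.2.2 makes it a trial objective to show that SAP is safe. That needs one counting window, the same in both arms and tied to randomisation, because the analysis is by randomised group. The outcome is tied to randomisation, but the rule that generates its data is tied to an event that happens in one arm only. If sites follow section 10.2 literally, the reported SAEs cannot fully supply the outcome in section 8.2.2, and the shortfall arises in the block arm between randomisation and insertion. Sites would also have to decide for themselves when reporting starts for a usual-care participant.

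The end of the window is unclear too. SAEs are collected to the end of follow-up, but the outcome stops at discharge. An analyst cannot tell from the protocol whether SAEs after discharge are part of the safety comparison. Finally, the outcome's name covers complications in general, while its measure covers serious events only.

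**Working it through.** The protocol gives no figure to reproduce here. The check sets the sections side by side.

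**1. The two windows.** Let R be randomisation, I the day the trial intervention starts, D discharge and F the end of follow-up.

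- Outcome window (8.2.2): R to D.
- Reporting window (10.2, 10.4.1): I to F. Section 14.3 fixes the last analysed time point: "This analysis will include data items up to and including the 3 month assessment and no further".
- Inside the outcome but outside reporting: R up to I.
- Inside reporting but outside the outcome: D to F, for anyone discharged before 3 months.

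The mismatch at the end is one of definition. The data exist, and an outcome that stops at discharge can be cut from them. The mismatch at the start is one of capture, because events between R and I need not be reported.

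**2. Who has a start day I?**

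- Usual care: section 10.3 uses the term trial intervention for SAP, section 9.1.3 collects an insertion time and nothing equivalent for usual care, and section 7.1 describes usual care as local practice without a start event. With 1:1 allocation this concerns 824 / 2 = 412 participants.
- SAP arm, catheter not placed: section 9.1.3 foresees that insertion may fail. These participants have no insertion day either.
- SAP arm, catheter placed: I is the day of insertion.

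**3. Can I fall after R?** Yes. Table 1 marks randomisation on Day 0 and insertion under Days 1-5. Section 5 asks for randomisation and treatment by the next working day after consent at the latest, so a long lag is not intended, but a lag over one or more calendar days is possible. There are two limits. Section 9.1.3 counts Day 1 from the time of randomisation, and section 10.2 counts from the day of the intervention, so a catheter placed on the day of randomisation loses nothing.

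**4. Deadline.** Table 4 lists insertion-site infection and sepsis among the non-expedited SAEs. If a site learns of one in the first week, section 10.4.2 lets it wait for the 3-month form, whereas Table 9 makes it overdue after 4 weeks. A site relying on the 3-month option would breach Table 9.

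**5. Non-serious events.** Section 10.3 exempts them from reporting, while sections 9.1.3 and 9.1.4 and Table 1 list adverse events as collected data. The reason given in section 10.3 is that major trauma brings many well-understood events. That reason fits events due to the injury. It does not fit events due to the block, which section 1.2 describes as a new technique and which the Trial Summary outcome is meant to cover.

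**The case against.** The strongest reply is that the text can be read coherently. A reporting period may be wider than an outcome period, so running to the end of follow-up does not contradict an outcome that ends at discharge. Section 9.1.2 covers all participants and has monitoring begin once they are randomised and the allocated treatment starts. Section 7.1, headed as the trial intervention, includes usual care as a subsection. On that reading both arms start at about randomisation. Limiting AE reporting is also a reasoned choice in a non-CTIMP assessed as low risk.

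Much of this stands. The later end of reporting loses no data, and sites may well start at randomisation in practice. But section 9.1.2 sends the reader to section 10, whose stated rule starts with the intervention and whose own usage ties that term to SAP. The coherent reading has to be inferred, and a literal reader would reach a different one.

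A reader might infer that non-serious block complications will never reach the trial dataset. The documents do not support that. Adverse events are listed as collected data, insertion failure and removal within 24 hours are recorded (7.1, 9.1.3), insertion-site infection and anaesthetic toxicity are listed as SAEs to report (Tables 4 and 5), and the medically significant criterion in Table 2 can admit others. What is supported is a contradiction between section 10.3 and the schedule.

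A reader might also conclude that the deadline conflict would seriously delay the DMC. That has little force: the DMC is due to meet at least annually (16.6) and may request SAEs at its meetings (10.5.1).

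**Conclusion.** The concern holds as a set of contradictions in the current text. The safety outcome and the reporting period differ at both ends. The reporting start is not clearly defined for usual-care participants or for block-arm participants without a catheter. Block-arm SAEs before the day of insertion count in the outcome but need not be reported under section 10.2. The non-expedited deadline and the status of non-serious events are each stated in two incompatible ways.

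The size cannot be given as a number of events. It is tempting to express the lag as a share of the hospital stay, but the protocol states no usual lag, length of stay or SAE rate, so any percentage would rest on assumptions alone. Nor do the documents show that SAE rates will in fact be compared over different periods. That follows only if section 10.2 is applied literally in preference to sections 8.2.2 and 9.1.2. Events before insertion also cannot be complications of the catheter, so what is at risk there is comparability between arms, not detection of catheter harm.

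This should be corrected. It does not touch the primary outcome, but a stated objective lacks a single usable definition and the remedy costs very little.

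**What to change.** 1. In sections 10.2 and 10.4.1, start SAE reporting at randomisation in both arms, whether or not a catheter is placed, and align section 9.1.2 with this.
2. In section 8.2.2 and section 10, state one end point for the safety outcome, the same in both arms: either discharge, or the 3-month visit to which SAEs are already collected. If discharge is kept, say that later SAEs are reported but not counted in this outcome.
3. Give one deadline for non-expedited SAEs in both section 10.4.2 and Table 9.
4. Reconcile section 10.3 with sections 9.1.3 and 9.1.4, Table 1 and the outcome named in the Trial Summary. One way is to keep the exemption for unrelated non-serious events and record those rated possibly, probably or definitely related to the block, using the existing Table 6 categories. The daily form runs only to day 30 or discharge, so if the 3-month end point is chosen, the follow-up forms need the same field.

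The cost is protocol wording, a small form change if related events are recorded, and slightly more data entry at sites.

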# 9. TRIAL PROCEDURES

## 9.1. SCHEDULE OF ASSESSMENTS

#### 9.1.1.Screening

Details of the screening are described in section 6.1, screening assessments will include:

- Daily review of patients who have suffered blunt chest trauma
- Review of the patients medical records
- Confirmation of eligibility criteria
- Completions of screening logs

#### 9.1.2.Baseline (Day 0: within 48 hours of randomisation)

Once consent has been obtained, the following will be recorded prior to randomisation and participant receiving the allocated intervention:

- Relevant medical history (pre-admission details; treatments given to fractures prior to hospital admission)
- Charleson Comorbidity Index
- Basic demographic data
- Details of injury
- Current medication (concomitant medication; analgesic medication; other medication/treatments)
- Routine Assessments:
  - Injury severity scores (Abbreviated injury scale (AIS), frailty score, CPIS, Sequential organ failure assessment (SOFA))
  - ICU and/or hospital admission status
  - Mechanism of injury (pulmonary contusion, anatomical location of fracture, presence of flail segment) and details of other injuries on body
  - Overview of analgesic and other medication
  - Body temperature at hospital
  - Lung function assessments including FEV1 and FVC
  - Chest x-ray (CXR) interpretations, if any (new or progressive infiltrate characteristic of pneumonia or a new consolidation)
  - Tracheal secretions
  - Oxygenation
  - A pregnancy test will be carried out on patients of childbearing potential age, as per usual care
  - o CPIS
  - Covid-19 diagnosis and treatment
- Routine laboratory tests: (WBC; white cell count, CRP; C-reactive Protein; culture of tracheal aspirate)
- EQ-5D-5L
- Rating of pain (VAS)
- Blood samples (see section 9.1.5)

The participant will be randomised, and the allocated intervention will begin. The site research team will start to monitor and record any AEs and SAEs as described in section 10.

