# 5. CONSENT

Potential participants with MRF will, by default, be critically ill due to the effects of sedation, possible infection and possible delirium and, therefore, may lack the capacity to consent for themselves. Sites should follow the appropriate consent procedure depending on the potential participant's mental status. Where the potential participant lacks the capacity to consent for themselves, advice will be sought from a consultee (for sites in England and Wales; see section 5.1.2) or consent will be sought from a legal representative (for sites in Scotland; see section 5.1.5. Contact with the potential participant, consultee, or legal representative, to initiate the consent process should be made as soon as practically possible after the initial emergency has passed, taking the utmost care and sensitivity in doing so.

The Principal Investigator (PI) or delegate(s) are responsible for obtaining written informed consent for each participant and/or advice from a consultee or consent from a legal representative. Consent may also be taken by other members of staff at the site (e.g. Research Nurse or Allied Health Professionals) if local practice allows, and this role has been delegated by the PI on the Site Signature and Delegation Log.

Given the urgent nature of the condition, randomisation and intervention should occur on the same or next working day after consent has been taken.

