# 6. RECRUITMENT, ENROLMENT AND RANDOMISATION

# 6.1. SCREENING AND IDENTIFICATION

All patients who have suffered blunt chest trauma with MRF admitted to ward and critical care will be screened daily for eligibility. The site research team, who form part of the patient's clinical care team, will review patient's medical records to ascertain whether the patient meets the eligibility criteria. This process may be assisted by the Research Nurses/Practitioners employed or who hold an honorary contract with the site.

A medically qualified doctor, or an appropriately qualified healthcare professional, who has been delegated the task on the Site Signature and Delegation Log will confirm eligibility before randomisation. Potential participants who are deemed eligible will be approached by their clinical care team for consent as described in section 5. The patient will then be randomised and baseline data will be collected.

Details of all patients approached about the trial will be recorded on the Participant Screening/Enrolment Log, which will include data on the number of patients meeting the inclusion criteria but not entered into the trial and reasons for non-enrolment. The Participant Screening/Enrolment Log will be kept in the ISF, and should be available to be sent to the ERASER Trial Office upon request.

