#### 9.1.5.Blood sampling for future research

In anticipation of future studies, blood will be collected and spun from participants who have provided consent (either for themselves or where consent/ an opinion has been sought from a legal representative or consultee). These samples will be taken within 24 hours of randomisation, day 5 ( $\pm$  24h) and day 14 ( $\pm$ 24h) if the participant is still admitted and at discharge. The blood sample should be stored at -80°C, and eventually shipped in batches to the laboratory at the University of Birmingham. Full instruction of sample preparation and shipment will be available in a separate Work Instruction.

	Screening	Baseline	Days during hospital			ital	At discharge	Months post- Randomisation	
Visit	-	Day 0	1-5	6-13	14	15+	-	1	3
Time window	$\leq$ 72 hours	$\leq$ 48 hours		Dail	у		± 6 hours from discharge	± 7 d	ays
Eligibility check	х								
Valid informed consent		х							
Relevant medical history		х							
Basic demographic data		х							
Charleson Comorbidity Index		х						Х	х
Current medication		х	х	х	х	х	Х	Х	х
Date & time of injury		х							
Covid-19 diagnosis and treatment		х							
ICU/Ward admission details		х	x	х	x	x	x		
Randomisation		х							
Intervention insertion			х						
Intervention removal			х	х	х	х			
Failure of Intervention		х							
Date of discharge							Х		
Routine physical exam:									
Pregnancy test		х							
Body temperature		х	х	х	х	х			
AIS		х							
Frailty score		х							
SOFA		х	х	х	х	х			
CPIS		х	х	х	х	х			

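### Sections 6.1 and 9.1.2 put baseline measurement and randomisation in opposite orders, and the 48-hour baseline window has no stated direction, so an open-label site could take changeable baseline measures after allocation

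*Protocol*

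**What the plan says.** Protocol section 9.1.2 sets the rule for baseline. After consent, "the following will be recorded prior to randomisation and participant receiving the allocated intervention". Its list includes the pain rating, EQ-5D-5L, FEV1 and FVC, SOFA, CPIS, the chest X-ray interpretation, temperature, routine bloods and research blood samples. The section closes with the next step: "The participant will be randomised, and the allocated intervention will begin". On its own, this is measurement first, allocation second, treatment third.

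Four other places bear on timing:

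- Section 6.1, after eligibility and consent: "The patient will then be randomised and baseline data will be collected".
- The heading of 9.1.2: "Baseline (Day 0: within 48 hours of randomisation". Table 1 repeats a baseline window of 48 hours or less. Neither says before or after.
- Section 9.1.5, on the research bloods that 9.1.2 lists among the pre-randomisation items: "These samples will be taken within 24 hours of randomisation". Again there is no direction.
- Table 9 in 11.1.1, for the hospital admission and baseline forms: "Immediately following randomisation (Day 0". The column is headed "Schedule for submission".

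Section 6.3 states that neither patients nor investigators are blinded. Section 5 says that "randomisation and intervention should occur on the same or next working day after consent has been taken".

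**The concern.** A baseline value protects a comparison only if it was fixed before anyone knew the arm. Once the allocation is known, patients and staff can be influenced by it when rating pain or health state. Once a block is running, pain and lung function may already have changed, and this can happen in the SAP arm only. Baseline then differs between arms for a reason that randomisation does not remove.

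Three uses of baseline could be touched:

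- EQ-5D-5L is scheduled only at baseline, 1 month and 3 months. The cost-utility analysis in 15.2.1 covers 3 months, so baseline is the only utility value before 1 month.
- Pain and ventilatory function are secondary outcomes for which baseline is the natural reference.
- The primary outcome is a new diagnosis of pneumonia, and baseline CPIS and X-ray status are part of the picture of what was already present.

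The order of measurement is a site procedure. A statistical analysis plan cannot recover a pre-randomisation value that was never taken.

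**Working it through.** The protocol attaches no figure to this point, so the check is a comparison of the texts. The sample size (371 per group, 742 in total, 824 with 10% drop-out) uses only the assumed pneumonia rates, error rates and drop-out, and does not depend on when baseline is measured.

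**Step 1: order of events.** Section 9.1.2 runs consent, baseline, randomisation, intervention. Section 6.1 runs consent, randomisation, baseline. Both are written as instructions to sites and they cannot both be followed.

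**Step 2: does the window settle it?** Within 48 hours of randomisation can mean the 48 hours before or the 48 hours after.
- Read as before, it agrees with the 9.1.2 body text.
- Read as after, it agrees with 6.1. It would then overlap the daily outcome data, because 9.1.3 counts Day 1 from randomisation and records pain every 4 hours on Days 1 to 5.
- Table 1 does not decide between them. Its Day 0 column also holds randomisation itself and failure of intervention, and the second can be known only after allocation. The column is therefore not purely pre-randomisation.

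The heading is ambiguous. It does not by itself contradict the body text.

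**Step 3: can late measurement fall after the block?** Section 5 expects randomisation and intervention on the same or next working day after consent. A 48-hour window running forward from randomisation can therefore include time with the block in place. This is a possibility that the wording allows, not an instruction.

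**Step 4: which items are protected?** Section 6.2.2 requires every item on the Randomisation form before allocation. The minimisation variables (gender, age, centre, pulmonary contusion, displacement, fracture location, flail segment) are therefore fixed beforehand. Section 14.2 names only these for adjustment, so the stated covariates are not exposed. The protocol describes no equivalent check for pain, EQ-5D-5L, FEV1/FVC, SOFA, CPIS or the X-ray reading.

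**Step 5: Table 9.** It governs when forms are submitted. The Trial Number is allocated only at randomisation (6.2.2), so a baseline recorded beforehand and submitted straight afterwards satisfies both Table 9 and 9.1.2. Table 9 is not in conflict.

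**Result.** There is one direct contradiction (6.1 against 9.1.2) and two windows without direction (48 hours in the 9.1.2 heading and Table 1, 24 hours in 9.1.5). The minimisation covariates and Table 9 are not affected.

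**The case against.** The strongest reply is that 9.1.2 is the dedicated baseline section and is explicit twice, at its opening and its close. Section 6.1 is about screening and may be no more than loosely worded. Read with the sentence beneath it, the 9.1.2 heading most naturally means the 48 hours before randomisation, and 6.1 says nothing about measuring after a block. This stands as far as intent goes: the sponsor's design is sound and the fault lies in the wording. It does not remove the contradiction, because a site that follows 6.1 literally is complying with the protocol.

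The reply on the primary outcome also carries weight. The committee is blinded and uses medical history and all available trial information (6.3, 16.7). Many CPIS inputs, such as temperature and white cell count, are routine records. An effect on the primary result is possible but unproven. Blinding the committee would not, however, correct a site-recorded baseline taken after allocation.

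A reader might go further and try to size the bias. Section 1.2 reports a pain fall after SAP from 2.42 to 1.14, or (2.42 − 1.14)/2.42 = 53%. One could then assume that a share q of SAP-arm baselines is taken late and that baseline has slope b, so that an adjusted effect D becomes D − b·q·D. The protocol does not support this. It gives neither q nor b and states no pain model adjusted for baseline pain. The 53% is an uncontrolled before-after change on a 0 to 3 scale, whereas the trial uses 0 to 10. A reader might also infer that late baselines will occur. The text shows only that one passage permits them.

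**Conclusion.** The contradiction between 6.1 and 9.1.2 is certain from the text, and the missing direction in the 48-hour and 24-hour windows leaves it unresolved. The consequence is a route to bias in the changeable and subjective baseline measures. Baseline EQ-5D-5L and pain are the most exposed, then lung function, with a possible but unproven effect on baseline CPIS and X-ray status. The size cannot be computed from the protocol: it depends on how many sites follow 6.1, how late they measure and how each baseline enters the analysis, none of which is stated. The sample size and the planned covariate adjustment are untouched. The point should be corrected, since the remedy is cheap and a baseline not taken in time cannot be recovered. It does not show that the primary comparison is invalid.

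**What to change.** Reconcile the passages to the rule that 9.1.2 already states:

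- Reword 6.1 so that baseline is measured first and the patient is then randomised.
- State in the 9.1.2 heading and in Table 1 that the window is the 48 hours before randomisation.
- Give the baseline blood sample in 9.1.5 a direction, consistent with its place in the 9.1.2 list.
- Add a time stamp to the changeable measures (pain, EQ-5D-5L, FEV1/FVC, SOFA, CPIS and its components, X-ray reading) so that any taken after randomisation can be identified. History and injury details may be entered later.

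Table 9 needs no change. How a late value is handled in the analysis can be left to the statistical analysis plan. Setting every such value to missing is debatable, since it would also discard values taken after randomisation but before the block.

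The cost is a wording amendment and a time field on the baseline form. The downside is small: some bedside measurement must be finished before randomising patients who may be very unwell or lack capacity, and some baselines may be missing as a result.
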